4.2.2 SECONDARY ENDPOINTS

Change in mood score using PHQ-9 score Change in minute ventilation during HCVR testing Change in slope of HCVR Difference in duration of abnormal breathing in periictal period Difference in oxygen saturation during periictal period Difference in CO₂ level in periictal period

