4.2.3 EXPLORATORY ENDPOINTS

Change in VRTCO₂ Change in time to VRTCO₂ Change in time to end of HCVR testing

Version 01.2 Protocol:201607761 Version 20.2 Version 01.2

We will compare all the secondary outcome and exploratory measures using generalized linear models (GLMs), specifying an identity link for normally distributed data and the log link for right-skewed data.

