10.4.3 ANALYSIS OF THE SECONDARY ENDPOINT(S)

Observations with missing data are dropped from those analyses involving data variable.

Change in mood score using PHQ-9 score

This will be analyzed as the difference in PHQ-9 scores from baseline to final measurement between drug and placebo. The mean and standard deviation estimates of the differences will be provided.

Change in minute ventilation during HCVR testing:

This will be analyzed as the difference in minute ventilation during HCVR testing from baseline to final measurement between drug and placebo. The mean and standard deviation estimates of the differences will be provided.

Change in slope of HCVR

This will be analyzed as the difference in slope of HCVR between drug and placebo. Using a linear mixed model, we will include a predictor that is the interaction between HCVR slope and the treatment group. The mean and standard deviation estimates of the differences will be provided.

Difference in duration of abnormal breathing during periotal period:

Mean duration of abnormal breathing during perictal periods between drug and placebo will be compared. The mean and standard deviation estimates of the differences will be provided.

Difference in oxygen saturation during periotal period

Mean drop in oxygen saturation during perictal period between drug and placebo will be compared. The mean and standard deviation estimates of the differences will be provided.

Difference in CO₂ level in periotal period

Mean change in CO₂ level in periocal period compared to pre seizure baseline will be compared between drug and placebo. The mean and standard deviation estimates of the differences will be provided.

All the secondary outcome measures will be estimated using generalized linear mixed models (GLMMs), specifying an identity link for normally distributed data and the log link for right-skewed data.

Since we are interested in obtaining estimates for future studies, we will not run non-parametric analyses, which only provide p-values.

Version 01.2 Protocol:201607761 Version 20.2 Version 01.2

Assessment of adverse events

All the adverse events will be recorded. Frequency of each adverse events will be compared between the two groups and tested using one tail t-test with type I error at 0.025

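### As written, the mixed-model sentence for change in HCVR slope does not return the between-arm difference in change; the link rule and model class also need tidying (minor)

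*Combined protocol and SAP*

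**What the plan says.** Section 4.2.2 lists "Change in slope of HCVR" as a secondary endpoint. The protocol summary and section 4.1 agree with it: each subject's post-treatment test is set against baseline, and the before-after change is compared between arms.

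Section 10.4.3 then gives the analysis: "Using a linear mixed model, we will include a predictor that is the interaction between HCVR slope and the treatment group". The sentence before it speaks only of a slope difference between drug and placebo. For PHQ-9 and minute ventilation, the same section does say baseline to final measurement. The slope paragraph ends: "The mean and standard deviation estimates of the differences will be provided".

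Two general rules sit alongside:

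- Model class. Section 10.4.3: "All the secondary outcome measures will be estimated using generalized linear mixed models (GLMMs"). Section 4.2.3: "We will compare all the secondary outcome and exploratory measures using generalized linear models (GLMs").
- Link, in both sections: "specifying an identity link for normally distributed data and the log link for right-skewed data". No distribution family is named and no outcome is excepted. Through section 4.2.3 the rule also reaches exploratory changes such as "Change in time to end of HCVR testing".

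For the peri-ictal endpoints, section 10.4.3 says: "Mean duration of abnormal breathing during perictal periods between drug and placebo will be compared". It does not say whether the unit is the seizure or one mean per subject.

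**The concern.** HCVR slope is the outcome, and is itself a regression slope of ventilation on CO2. Entered as a predictor interacting with treatment, it answers a different question from how much more the slope changed on fluoxetine than on placebo. An analyst must supply the response, the visit structure and the baseline term, and different choices give different answers. Section 10.1 says the pilot exists to supply figures for planning later studies, so a model estimate that could be none, half or all of the drug effect is a poor one to pass on.

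The two general rules raise lesser problems. A log link needs a positive mean, whereas a change score can be zero or negative. A GLM on several seizures per subject, taken as independent, would give too small a standard error.

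**Working it through.** The plan gives no effect size, SD or sample-size calculation for this endpoint, so there is no stated figure to reproduce.

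**Inputs from the documents.** Baseline slope below 2.0 L/min/mmHg (section 4.1). One baseline and one repeat HCVR test (section 7.3.3). 40 subjects randomized 1:1 (protocol summary), or 20 completers for the HCVR part (section 4.1).

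**Assumed inputs.** Constant drug effect 0.50 L/min/mmHg; screening slope normal with mean 2.2 and SD 0.8; test-retest correlation (ICC) 0.5 to 0.9.

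**Step 1: what each reading estimates.** The arms have equal expected baseline slope by randomization. Simulated values are from 4000 trials at ICC 0.7, given as 40 subjects; 20 subjects.

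| Reading | Expected | Simulated |
|---|---|---|
| Change on baseline slope × treatment, interaction term | 0 | 0.003 (SE 0.462); −0.020 (SE 0.718) |
| Ventilation on CO2 × treatment, both tests pooled | (0 + 0.50)/2 = 0.25 | 0.249; 0.250 |
| Difference at follow-up only | 0.50 | 0.498; 0.498 |
| Change on treatment | 0.50 | 0.499 (SE 0.185); 0.495 (SE 0.266) |
| Follow-up slope on treatment and baseline slope | 0.50 | 0.499 (SE 0.183); 0.495 (SE 0.267) |

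The follow-up-only reading is right on average but carries any chance baseline difference in full. In a second simulation, with a true effect of 0.40 and a baseline imbalance of about −0.2, it gave 0.201 while the difference in change was 0.397. In the same set-up without imbalance, ventilation on CO2 × visit × treatment returned 0.400 as its three-way term.

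The zero and the half follow from the structure of the models, not from the assumed SDs.

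**Step 2: precision of baseline adjustment.** Truncating the screening distribution at 2.0 gives a baseline mean of 1.429 and variance V = 0.200. With ICC ρ, the variance of change is (1−ρ)²V + 0.64(1−ρ²), and the adjusted residual variance is 0.64(1−ρ²). Estimating the baseline coefficient multiplies the latter by about 1 + 1/(N−4).

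- ρ = 0.5, N = 40: (0.480/0.530) × 1.028 = 0.93, a gain of 7%.
- Simulated ratios at ρ = 0.5, 0.7, 0.9: 0.93, 0.98, 1.02 with 40; 0.97, 1.01, 1.04 with 20.

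**Step 3: log link on placebo slope change.** Selecting low baselines brings regression to the mean, so the expected placebo change is (1−ρ)(2.2 − 1.429). At ρ = 0.7 this is 0.231, with SD √(0.018 + 0.326) = 0.587, so d = 0.231/0.587 = 0.394. The chance that an arm mean is ≤ 0 is Φ(−d√n):

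- n = 20 per arm: Φ(−1.76) = 4%; across ρ = 0.5 to 0.9, about 1 to 17%.
- n = 10 per arm: Φ(−1.25) = 11%; across the same range, about 4 to 25%.

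A Gaussian log-link model fails in those data sets: in a check on right-skewed data, it recovered both arm means whenever the placebo mean was positive and never otherwise. A gamma log link fails as soon as one individual change is ≤ 0. At ρ = 0.7 the share of such placebo changes is Φ(−0.394) = 35%, so with 10 per arm at least one is expected in 1 − 0.65¹⁰ = 99% of data sets.

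**Step 4: seizures treated as independent.** With k seizures per subject and within-subject correlation r (assumed 0.3 to 0.7), the SE is too small by √(1 + (k−1)r). For k = 3 this is 1.26 to 1.55. If counts vary as 1 + Poisson(2), again averaging 3, k is replaced by E(k²)/E(k) = 11/3, giving 1.34, 1.53 and 1.69 at r = 0.3, 0.5 and 0.7. Simulation with 10 subjects per arm (6000 trials) gave 1.36, 1.57 and 1.72. A fair summary is 1.3 to 1.75.

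**The case against.** The sentence may be no more than loose wording for a slope-by-group comparison. Its paragraph is headed as a change, and the protocol summary and sections 4.1 and 4.2.2 all describe change, which also counts against the pooled reading. This is a fair account of intent, but it does not supply the missing visit or baseline term: someone following section 10.4.3 as written would not fit the model that the endpoint needs.

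The practical harm is small, and this stands in full. Section 10.4.1 rules out inferential tests, section 10.2 states no hypothesis, and the mean and SD of the differences do not depend on the model. A reader might infer that the endpoint cannot be estimated at all; the documents do not support that.

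A reader might also infer that the log link would fail half the time. That figure needs a true mean change of zero. For slope, selection below 2.0 makes the expected placebo change positive, and the rule applies only if the score is judged right-skewed, which nothing in the documents predicts.

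Nor does the plan say that seizures will be treated as independent. Section 10.4.3 specifies mixed models, and what it promises is means and SDs, not standard errors. What remains is that section 4.2.3 names a different model class and the unit is not stated.

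Finally, baseline adjustment is partly a preference. Naming the missing terms within the plan's own mixed model would repair the sentence equally well.

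**Conclusion.** Minor, but wrong as written for the model-based estimate of change in HCVR slope. Followed literally, the term has expectation 0 under a constant drug effect; with both tests pooled, it gives half the effect. Neither is the between-arm difference in change that the protocol defines. These two results need only a constant effect, randomization and one test before and after treatment; the effect of 0.50 is illustrative.

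The link rule is a conditional fault: it bites only if a signed change score is judged right-skewed, and how often it then fails depends on the family, which is not stated. The difference in model class matters only when several tests or seizures per subject enter. The percentages and SE factors for these two points rest wholly on assumed inputs.

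**What to change.** Replace the slope sentence in section 10.4.3 with: *Follow-up HCVR slope will be modelled on treatment group and baseline slope, and the adjusted fluoxetine-minus-placebo difference reported beside the mean and SD of change by arm.* Equivalently, to stay within the mixed model, fit ventilation on CO2 × visit × treatment with subject random effects and report the three-way term.

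In sections 4.2.3 and 10.4.3:

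- Use the identity link for every signed change score: PHQ-9, minute ventilation, slope, peri-ictal CO2 change and the three exploratory changes. Keep the log link for strictly positive outcomes such as duration of abnormal breathing, and name the family.
- State one model-class rule: a GLM for one value per subject, and a subject random effect whenever several tests or seizures per subject enter.
- State the unit of analysis for the peri-ictal endpoints.

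The cost is wording and one degree of freedom. Baseline slope is already measured for eligibility, and no visit, procedure or subject number changes. The change should not be presented as a gain in precision: with 20 subjects, baseline adjustment ranges from a 3% variance gain to a loss of about 4%.

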10.4 DESCRIPTION OF STATISTICAL METHODS

10.4.1 GENERAL APPROACH

Categorical data descriptive statistics will be presented as percentages, while continuous data descriptive statistics will be presented with the mean and standard deviation. Due to our goal of establishing estimates of centrality and spread for various measures to be used in future studies, no inferential tests will take place in this study.

Version 01.2 Protocol:201607761 Version 20.2 Version 01.2

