10.4.6 BASELINE DESCRIPTIVE STATISTICS

We plan to compare the baseline descriptive statistics between the treatment and control groups and establish if there is a significant difference of any variables. For continuous variables, a two sample t-test will be used to compare data that appear to be normally distributed (Wilcoxon Rank Sum test for skewed data). For categorical data, Pearson's Chi-square test of independence will be used.

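### Section 10.4.3 rules out rank-based methods for a reason that is untrue, and the plan promises no interval for any rate or between-arm difference

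*Combined protocol and SAP*

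**What the plan says.** Section 10.1 describes the study as a pilot meant to supply estimates for later studies. Section 10.4.1 sets the general rule that "continuous data descriptive statistics will be presented with the mean and standard deviation", and adds that "no inferential tests will take place in this study". Section 10.4.2 reports enrollment and retention as numbers per 3 months and as percentages of patients screened.

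For each secondary endpoint, section 10.4.3 promises that "The mean and standard deviation estimates of the differences will be provided". It also says that all secondary outcomes will be estimated with "generalized linear mixed models (GLMMs), specifying an identity link for normally distributed data and the log link for right-skewed data". Section 4.2.3 makes the same provision with generalized linear models and extends it to the exploratory measures. Section 10.4.3 then gives the aim, "Since we are interested in obtaining estimates for future studies", and concludes from it that "we will not run non-parametric analyses, which only provide p-values".

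No section names a confidence interval, standard error, median or quartile for any endpoint, or a distribution family for the models. Section 10.4.6 allows the "Wilcoxon Rank Sum test for skewed data" when baseline characteristics are compared.

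**The concern.** The exclusion rests on an error of fact, and the error works against the aim given in the same sentence. Rank-based methods offer an estimate of shift with an interval, so a wish for estimates is no reason to leave them out. The plan expects that some outcomes may be right-skewed, which is where such summaries help most.

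The missing intervals are a related gap. A later team would take recruitment and retention rates, between-arm differences and SDs from this pilot to plan its own trial. At this sample size those quantities are imprecise, and the SAP can be followed to the letter without that imprecision being reported.

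**Working it through.** The documents give no effect size, SD, power or calculated sample size, so there is no statistical figure to reproduce. The checks below concern precision and whether the stated reason is true.

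**1. Numbers per arm.** Section 10.6.1 sets 20 participants per location at 1:1, and 2 × 20 = 40 agrees with the Protocol Summary. On-treatment peri-ictal data come only from the clinic cohort (sections 4.1 and 7.3.3), so 20 / 2 = 10 per arm. The number may be lower, since section 10.4.3 drops observations with missing data.

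**2. Precision with no skew at all.**
- 95% half-width for a difference in means = t(0.975, 2n − 2) × √(2/n) × SD. For n = 10: 2.101 × 0.447 = 0.94 SD. For n = 5: 1.46 SD.
- 95% limits for an SD = s × √(df / χ²). Pooled over two arms of 10 (df 18): 0.76 to 1.48 times s. Over two arms of 20 (df 38): 0.82 to 1.29 times s. Squared, these correspond to a 0.57- to 2.19-fold or 0.67- to 1.66-fold range in the sample size of a later trial.

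**3. The feasibility rates.**
- Recruitment: 40 randomized at the anticipated 2 per month (section 5.3) takes 20 months. Exact Poisson limits for 40 events are 28.6 and 54.5. Divided by 20, they give 1.43 to 2.72 per month.
- Retention: suppose 34 complete (an illustrative count). With 40 randomized as the denominator this is 85%, Wilson 95% interval 71% to 93%. With about 100 screened (section 5.3), which is the denominator that section 10.4.2 names, it is 34%, interval 25% to 44%. The denominator therefore has to be stated beside the interval.

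**4. Does a rank method give only a p-value?** Take invented durations in seconds:
- drug: 40, 45, 50, 55, 60, 65, 70, 75, 80, 300
- placebo: 45, 50, 55, 60, 65, 70, 75, 80, 85, 90

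The Hodges-Lehmann shift is the median of the 100 pairwise differences, −5.0 s. Its exact rank-based 95% interval runs from the 24th smallest to the 24th largest difference, −20 to 15 s. So there is an estimate and an interval. The mean difference is 84.0 − 67.5 = +16.5 s. Without the value of 300 it is 60.0 − 67.5 = −7.5 s, and the drug-arm SD falls from 77.0 to 13.7.

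**5. How much would skew matter?** The documents give no distribution, so I assumed lognormal data with 10 per arm.

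| Log-scale SD | Largest value as share of arm total (median) | Fall in arm mean if it is removed (median) | Sampling SD of mean difference ÷ that of Hodges-Lehmann |
|---|---|---|---|
| 0.5 | 19% | 10% | 1.2 |
| 0.8 | 25% | 17% | 1.6 |
| 1.0 | 30% | 22% | 2.1 |
| 1.2 | 34% | 27% | 3.1 |

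With normal data the last ratio is 0.97. At log-SD 0.75 and 1.0, the 5th to 95th percentiles of sample SD over true SD are 0.37 to 1.75 and 0.26 to 1.85. Dependence on single values is thus modest under mild skew and large under strong skew. A log link on the arithmetic mean helps only in part: over log-SD 0.5 to 1.2, the log ratio of means has a sampling SD of 0.24 to 0.68, against 0.22 to 0.54 for the log ratio of geometric means.

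**6. Limits of the remedies.**
- Hodges-Lehmann has a different target from the mean difference unless the effect is a pure shift. With lognormal data, placebo median 1 and an assumed ratio of means of 0.6, it averages about −0.38 to −0.39, while the true mean differences are −0.53 (log-SD 0.75) and −0.66 (log-SD 1.0).
- Chi-square limits for an SD assume normality. Under the same lognormal data, a one-sided 80% upper limit for the pooled SD (1.18 × s at df 18, 1.12 × s at df 38) covers the true SD only about 50% (log-SD 0.75) or 38–39% (log-SD 1.0) of the time. The two-sided 95% interval covers it 39% to 62% of the time.

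**The case against.** The best reply is that skew already has a planned model. The sentence just before the exclusion commits to "specifying an identity link for normally distributed data and the log link for right-skewed data", and a fitted model yields a standard error. This stands. A reader might infer that the plan rests on raw means and SDs with no provision for skew, and the documents do not support that. What remains is narrower: no family is named, and no interval from the model is promised.

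Second, a reader with the mean, SD and n can work out an approximate standard error, and the rates can be treated likewise from their counts. That is also true, so the information is unreported rather than destroyed. For strongly skewed data, though, such back-calculation is unreliable.

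Third, the degree of skew is my assumption. A reader might infer that the peri-ictal results will hinge on one or two long events. The documents give no distribution, and nothing in them shows that the fall in oxygen saturation or the change in CO₂ is skewed. The possibility is most plausible for duration.

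A reader might also infer that seizures with normal breathing score zero and would be lost from a gamma model. The plan states neither that scoring rule nor a gamma family, so the inference has no footing.

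Finally, the Wilcoxon test in section 10.4.6 is used there as a test. That fits the plan's mistaken view of rank methods, so it is not a strong contradiction.

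**Conclusion.** The point holds in a limited form. The reason given for excluding non-parametric analyses is wrong and runs against the plan's own estimation aim; this needs no assumption about the data. The absence of any promised interval is also plain from sections 10.4.1 to 10.4.3, and it matters at about 10 per arm even for normal data. The claim that a mean and SD can depend heavily on one or two values is conditional on strong right skew, and the figures for it come from an assumed lognormal range.

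The severity is minor to moderate. Apart from the feasibility rates, the point concerns secondary endpoints of a pilot without efficacy tests, but their estimates and SDs are what the pilot hands on.

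**What to change.** - Delete the sentence in section 10.4.3 that excludes non-parametric analyses.
- For endpoints that prove skewed, report median and quartiles by arm beside the mean and SD. Add the Hodges-Lehmann shift with its 95% interval, on one value per participant, as a supplement to the model-based mean comparison and not a replacement for it.
- Name the distribution family of the models, and report every between-arm difference, including the model estimates, with a 95% interval.
- Report 95% intervals for recruitment (Poisson) and retention (Wilson, with the denominator stated).
- For approximately normal endpoints, give the SD with its chi-square interval. For skewed endpoints, do not use chi-square limits or a planning multiple such as 1.12 × s or 1.18 × s. Give the SD on the log scale, or a bootstrap interval labelled approximate.
- Amend the mean-and-SD rule in section 10.4.1 to match. Its statement that there will be no inferential tests can stay, because intervals are estimates.

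The cost is SAP wording and a few more table columns, with no extra participants or visits. The downside is that the pilot's uncertainty will be visibly wide.

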10.4.4 SAFETY ANALYSES

All the adverse events will be recorded. Severity and relationship to intervention will be determined as described in section 8. Frequency of each adverse events will be compared between the two groups and tested using one tail t-test with type I error at 0.025.

Adverse events leading to premature discontinuation from the study drug and serious treatment-emergent AEs should be presented either in a table.

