2 INTRODUCTION: BACKGROUND INFORMATION AND SCIENTIFIC RATIONALE

2.1 BACKGROUND INFORMATION

Sudden unexpected death in epilepsy patients (SUDEP) ranks second only to stroke among neurological diseases in years of potential life lost (YPLL). While the specific mechanisms of death in SUDEP are not well understood, per-ictal respiratory dysfunction likely plays an important role in many cases. Seizure related respiratory depression of variable severity is commonly observed, and on rare instances may be fatal. There is a gap in our knowledge regarding the mechanisms responsible for peri-ictal respiratory dysfunction. A better understanding of these mechanisms would open the door to interventions to decrease the risk of SUDEP.

Several lines of evidence support a critical role for the serotonergic system in central control of ventilation. Serotonin neurons in the raphe nuclei of the brainstem sense rising carbon dioxide and low pH, thereby stimulating breathing and arousal. These responses may serve as mechanisms that protect against asphyxia, particularly during sleep or the post-ictal state. In addition, data from animal and human studies also indicate that serotonin possesses independent anti-seizure properties. Finally, in mouse models of seizure-induced sudden death, pre-treatment with selective serotonin reuptake inhibitor (SSRI) agents prevents death following seizures. These observations led us to formulate our *central hypothesis*: that a subset of epilepsy patients has impaired central chemo-responsiveness as tested by the ventilatory response to inhalation of carbon dioxide (hypercapnic ventilatory response, HCVR), and this correlates with a greater degree of peri-ictal respiratory depression, thereby increasing the risk of terminal cardiorespiratory dysfunction and death. We further hypothesize that the administration of fluoxetine (an SSRI agent) to patients with a depressed HCVR will enhance CO₂ sensitivity, and reduce the severity of peri-ictal respiratory depression.

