2.3.1 KNOWN POTENTIAL RISKS

Fluoxetine is a FDA approved antidepressant medicine which is used very frequently and safely. Some patients may experience some side effects that include: Nausea, diarrhea, anorexia, dry mouth, dyspepsia, insomnia, anxiety, nervousness, somnolence, tremor, decreased libido, abnormal dreams, headache, asthenia, flu like syndrome, fever, weight loss, Flatulence, constipation, rash, pruritus, abnormal vision etc. However, rare and serious side effects are also possible which include; worsening depression, increase suicidal thoughts or actions, mood swings, acting aggressive or violent, serotonin syndrome, severe allergic reaction- trouble breathing, swelling of face, tongue, eyes or mouth, rash, hives, abnormal bleeding if you are taking blood thinner coumadin warfarin (Coumadin®), a non-steroidal anti-inflammatory drugs (NSAIDs, like Ibuprofen or naproxen), or aspirin, increase in seizure frequency and possible irregular heart rhythm called Torsades de pointes due prolonged OT.

Fluoxetine is classified by FDA as category "C" for use in pregnancy which means there is a known risk of birth defect animal fetus but there are no adequate data and well-controlled studies in human. Stopping fluoxetine suddenly can cause serious symptoms including:

- Anxiety, irritability, high or low mood, feeling restless or changes in sleep habits
- Headache, sweating, nausea, dizziness
- Shaking, confusion etc

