• 2) To test effect of fluoxetine on peri-ictal respiratory depression: Subjects will be screened in neurlogy clinic from a group of previously diagnosed patients with epilepsy who are planned for VEEG study. Eligible subjects will undergo HCVR testing. Eligible subjects with a reduced baseline HCVR slope (<2.0 L/min/mmHg) will be enrolled and randomized to fluoxetine vs placebo (1:1) until a total of 20 subjects complete the study. Both the subjects and investigators will be blinded to the randomization process. A standard titration plan for fluoxetine & placebo will be as above, for 4 weeks prior to EMU admission. During EMU admission, the subjects will be monitored with VEEG, EKG, EMG, SpO₂, tcCO₂/ETCO₂, oral & nasal thermistor & pressure transducer to measure airway pressure, and RIP with abdominal & chest belts to measure change in circumference during respiration. Peri-ictal respiratory changes in the two groups will be compared to assess the effect of fluoxetine.

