7.3.3 FOLLOW-UP

Follow up phone call at end of week 1 and 3

Record for adverse events as reported by the participants.

If suspicious for mania, will perform full Altman self-report maniac scale

Record compliance to assigned treatment as reported by the participants.

Record current medication

Follow up visit 4 weeks (+/-1 week) after randomization

Record for adverse events as reported by the participants.

Record compliance to assigned treatment as reported by the participants and by counting pill from the pill container brought by the participants.

Record PHQ-9 score

Repeat HCVR testing

Record current medication

Video EEG study with comprehensive respiratory monitoring in EMU for paticipants enrolled at neurology clinic

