7.3.7 SCHEDULE OF EVENTS TABLE

Procedures	Screening	Enrollment	phone call	ronow up phone call	Follow up visit	r filal Yellow up phone call				
Informed consent	X									
Demographics	X									
Medical history	X									
Iowa SSRI	X									
Sscreening Questionnaire	Λ									

Version 01.2 Protocol:201607761 Version 20.2 Version 01.2

Procedures	Screening	Enrollment	phone call	phone call	Follow up visit at week 4	up phone call				
Pregnancy screening questionnaire & urinary pregnancy test	X				X					
Medication history	X		X	X	X	X				
Iowa SSRI study questionnaire		X								
HCVR testing	X									
PHQ-9 score		X			X					
Randomization		X								
Video EEG & respiratory monitoring in EMU	Xª	Xª			Xb					
Adverse events evaluation			X	X	X	X				
Assessment of compliance			X	X	X					

a: Subjects enrolled from EMU

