8.1.2 DEFINITION OF SERIOUS ADVERSE EVENTS (SAE)

An AE or suspected adverse reaction is considered "serious" if, in the view of the investigator, it results in any of the following outcomes: death, a life-threatening adverse event, inpatient hospitalization or prolongation of existing hospitalization, a persistent or significant physical or mental incapacity including worsening depression, increase suicidal thoughts or actions, acting aggressive or violent, or a congenital anomaly/birth defect. Important medical events that may not result in death, be life-threatening, or require hospitalization may be considered serious when, based upon appropriate medical judgment, they may jeopardize the patient or subject and may require medical or surgical intervention to prevent one of the outcomes listed in this definition. Examples of such medical events include allergic reactions including angioedema of face, tongue, mouth, and bronchospasm requiring intensive treatment in an emergency room or at home, or increased seizure frequency from baseline that do not result in inpatient hospitalization.

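### Seizure worsening is a named serious risk, but the plan compares it only as adverse-event frequency and uses no seizure count from the clinic cohort's on-treatment video-EEG

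*Combined protocol and SAP*

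**What the plan says.** **The risk.** Section 2.3.1 includes "increase in seizure frequency and possible irregular heart rhythm" among the rarer, serious effects of the drug. Section 8.1.2 gives as an example of a serious medical event "increased seizure frequency from baseline that do not result in inpatient hospitalization". Section 2.1 points the other way: "data from animal and human studies also indicate that serotonin possesses independent anti-seizure properties". The direction of any effect on seizures is therefore open.

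**The recording.** For the clinic route, section 4.1 says: "A standard titration plan for fluoxetine & placebo will be as above, for 4 weeks prior to EMU admission". Section 7.3.3 then lists, at the week-4 visit, "Video EEG study with comprehensive respiratory monitoring in EMU for paticipants enrolled at neurology clinic". In the schedule (7.3.7), the screening and enrolment video-EEG carries the footnote "a: Subjects enrolled from EMU". Those participants start study drug at discharge (4.1), so the schedule gives them no on-treatment recording. Section 7.1.2 classes video-EEG as standard of care.

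**The capture and analysis of harm.** Section 7.3.3 has adverse events recorded from participant report at the calls and the visit. Section 8.3 adds investigator inquiry at each contact, presentation for medical care and review by a monitor. Section 10.4.4 begins "All the adverse events will be recorded. Severity and relationship to intervention will be determined as described in section 8", compares the frequency of each event between groups, and tabulates serious treatment-emergent events.

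**What is not there.** Neither the endpoints (4.2.1 to 4.2.3) nor the analyses (10.4.2 to 10.4.4, 10.4.11) contain a seizure count or rate. Seizures appear only as the occasions on which breathing, oxygen saturation and CO₂ are measured.

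**The concern.** In an epilepsy trial, more seizures is the named harm most specific to the population. The adverse-event comparison counts reports of worsening, not seizures. A seizure seen on video-EEG need not become an adverse event, because 8.3 treats conditions present at screening as baseline and records only deterioration.

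The gap also affects the peri-ictal secondary endpoints. A peri-ictal duration, desaturation or CO₂ change exists only for someone who has a seizure while monitored, and 10.4.3 drops missing observations. Each arm's mean is therefore taken over a group selected after randomisation. If treatment changes who seizes or how often, the two means describe different selections, and the planned output does not reveal it.

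Section 10.1 says the pilot exists to provide estimates for later studies. Seizures per monitored day and the proportion with any seizure are figures that a later peri-ictal trial would need.

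**Working it through.** The plan has no figure to reproduce: 10.5 makes no sample size calculation, and no seizure rate is given anywhere. The check is a reading of the sections, followed by arithmetic on assumed rates.

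**1. Who has an on-treatment recording**

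| Cohort | Before treatment | After 4 weeks of drug or placebo |
|---|---|---|
| EMU-enrolled | Video-EEG (7.3.7, note a) | None scheduled |
| Clinic-enrolled | None scheduled | Video-EEG (4.1, 7.3.3, 7.3.7) |

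Section 10.6.1 puts 20 participants in each location, randomised 1:1, so 20 / 2 = 10 per arm at most have an on-treatment recording. A seizure count supports a between-arm comparison in the clinic cohort. It does not support change from baseline in either cohort.

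**2. Precision of a seizure rate ratio**

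Assumptions: n = 10 per arm, equal monitored time, true ratio 1, mean μ seizures per stay, negative binomial dispersion k.

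SE(log RR) = √[2(1/μ + k)/n], and the 95% factor = exp(1.96 × SE).

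With μ = 3:
- k = 0.5: SE = √(2 × 0.833/10) = 0.408, factor 2.23
- k = 1: SE = √(2 × 1.333/10) = 0.516, factor 2.75
- k = 2: SE = √(2 × 2.333/10) = 0.683, factor 3.81

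For μ from 1 to 5 and the same k, the factor runs from 2.1 to 4.6. For μ from 2 to 8 and k from 0.5 to 1.5, it runs from 2.0 to 3.5, and power for a true doubling (one-sided 0.025) is about 20% to 52%.

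**3. How many participants the peri-ictal means rest on**

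Under the same model, P(no seizure) = (1 + kμ)^(−1/k). The expected number of contributors out of 10 is 10 × (1 − P).

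| k | μ = 3 | μ = 6 (doubled rate) |
|---|---|---|
| 0.5 | 10 × (1 − 0.160) = 8.4 | 10 × (1 − 0.063) = 9.4 |
| 1 | 10 × (1 − 0.250) = 7.5 | 10 × (1 − 0.143) = 8.6 |
| 2 | 10 × (1 − 0.378) = 6.2 | 10 × (1 − 0.277) = 7.2 |

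A doubling takes expected seizures from 10 × 3 = 30 to 10 × 6 = 60, but adds only about one contributor. A table of peri-ictal means with the number contributing would barely show it.

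**4. What the adverse-event comparison can show**

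At 20 per arm and one-sided 0.025, with no events on placebo, Fisher's exact test needs 5 of 20 on fluoxetine (p = 0.0236). This is an illustration, since 10.4.4 names a t-test. No events in 20 is still compatible with a true rate up to 1 − 0.025^(1/20) = 16.8%.

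**5. Who could be missing from the recording**

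Section 8.1.2 makes seizure worsening a possible serious adverse event. Section 5.4.2 ends participation for serious adverse events, while 5.4.1 leaves that to the investigator. Section 5.4.2 also collects no outcome measures after a post-randomisation withdrawal, and 10.3 specifies a per-protocol set. Someone who worsens in weeks 1 to 4 may never reach the week-4 video-EEG.

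**The case against.** A reader might infer that this harm rests on participant report alone. The documents do not support that. Section 8.3 names other routes, the investigator judges seriousness (8.1.2) and the examining clinician grades causality (8.2.2). Routine capture is still participant report, and clinical monitoring is marked not applicable in section 9, so *mainly* is the accurate word.

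A reader might also infer that nothing in the results would reveal extra seizures. That goes too far as well. Recognised worsening would enter the between-group comparison in 10.4.4 and, if serious, the table. What is missing is a count or rate. Nor do the documents suggest that one arm will have more but milder seizures and so look better. That is one possibility the plan could not detect, not a predicted bias.

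The strongest objection concerns the remedy. A count restricted to monitored participants conditions on reaching week 4, which seizure worsening itself may prevent, so it could falsely reassure. It covers about half the trial, has no baseline, and is too imprecise for a test. Section 10.4.1 disclaims inferential testing, and this is a feasibility pilot. All of this stands. It means the count should be descriptive, with the unmonitored accounted for by arm. It does not justify leaving the count out.

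A more basic gap is also fairly raised: no listed procedure names a seizure diary or a baseline seizure frequency, although 8.1.2 measures worsening from baseline. A video-EEG table does not fill that gap.

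**Conclusion.** The concern holds in limited form. A named serious risk is compared only as adverse-event frequency, while on-treatment recordings from about 10 participants per arm yield no reported seizure count. The peri-ictal means therefore cannot be read against who seized and how often.

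The gain from the change is modest. Under assumed means and dispersions, the interval for a rate ratio is the estimate times or divided by about 2 to 4 (2.0 to 4.6 across every combination tried). It could exclude only large worsening. Those means and dispersions are assumptions; the documents give no seizure rate, dispersion or length of EMU stay. The 10 per arm also assumes that everyone randomised is monitored.

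A reader might expect video-EEG to give a clean randomised estimate of increased seizure frequency. It would not: there is no pre-treatment recording in the clinic cohort, and early termination may remove those who worsened. This is a cheap improvement worth making, not a defect that invalidates the pilot.

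**What to change.** Add to 10.4.4 a descriptive safety table, by arm, for the clinic cohort:

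- Video-EEG seizures, monitored time, and seizures per monitored day, counting participants with zero.
- Proportion of monitored participants with any seizure.
- Rate ratio with 95% CI, presented as an estimate and not a test. A negative binomial model with monitored time as offset is one suitable choice.
- Number randomised but not monitored, with reasons, including termination for seizure worsening.

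Report it for all randomised clinic-route participants, whatever the per-protocol set in 10.3. As 5.4.2 stands, those who withdraw before monitoring would appear in the not-monitored row.

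Label the table as an EMU, between-arm measure that does not estimate change from baseline and does not cover the EMU-enrolled cohort. State three limits beside it: the interval is wide, EMU rates may differ from rates at home, and the comparison may falsely reassure if those who worsened never reached monitoring.

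Separately, reconcile 5.4.1 and 5.4.2 on whether a serious adverse event may or must end participation, because that determines who can appear in the table.

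The cost is SAP wording, one table, and recording monitored time and seizure counts from standard-of-care video-EEG. Monitored time is not currently a listed data item. No dose or visit changes.
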